- 4.) Should study staff receive no reply within 2 weeks, staff members will call the patient on the phone to assess interest in the study and to describe the study over the phone. If the patient remains interested, staff will confirm eligibility and assess for exclusion criteria. If the patient remains interested and appears eligible, study staff will set up an appointment time to go through the consent procedures and conduct the initial study visit. We will then mail or e-mail participants a consent form to look over ahead of time, so that they may prepare questions for the first visit. Note: If a participant prefers to perform all study visits by phone, a consent form will be mailed to the participant. This will be reviewed over the phone, and if the patient remains interested, he or she will sign the consent form and mail it back to study staff at MGH. Once the signed consent form is received, study staff will mail study materials to the participant, and the participant will be called for the first study visit.

For potentially eligible patients who are enrolled in the MGH Research Options Direct to You (RODY) Program, we will directly contact them via phone to inform them about the project. RODY identifies patients who are willing to be contacted directly about research studies. Patients who have agreed to be contacted directly are identifiable through the RPDR search; each patient's RODY status is available in the demographics table included in the RPDR output.

Future Studies. For participants approached either inpatient or outpatient, we will inquire at the end of the screen about whether they are interested in being contacted for future studies. This will allow us to create a database for contacting patients regarding any research studies we conduct in the future.

IV. PARTICIPANT ENROLLMENT

A. Methods of Enrollment

We will enroll participants through the recruitment procedures, described above, and the informed consent procedures, described below.

B. Procedures for obtaining informed consent

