Finally, once a participant signs the consent form, the investigator will perform a focused review of the participant's medical record (including laboratory data) to again confirm that the patient has HF, and will consult with the study cardiologist in the event that there is any need for further clarification. If there is question about the patient's medical prognosis (to assess whether the patient has a condition likely to lead to death within 6 months) the study team will consult with the patient's inpatient or outpatient team and/or the study cardiologist. Participants will be asked to sign a release form at the time of consent to allow study staff to discuss their diagnosis and aforementioned medical variables during the study.

Partners Healthcare has an electronic system that lets the participants' study doctors know if they are admitted to a Partners Hospital, or if they visit a Partners Hospital Emergency Department. We will

use this system to ensure that the study doctors know about any possible problems or side effects participants experience while taking part in the study.

C. Treatment assignment/randomization

There is no randomization procedure required for this trial.

V. STUDY PROCEDURES

A. Study visits/evaluations (See Table 1)

Initial visit (Week 1; in person). The initial visit will occur in an MGH inpatient unit, in the outpatient cardiac clinic, in a designated private office within the CPRP suite (for those contacted via opt-out letter), or over the phone (if a participant prefers to not come to the hospital for an in-person visit). Participants will meet with a member of the study staff (the study “trainer”) and complete self-report questionnaires. These questionnaires assess optimism (Life Orientation Test-Revised; LOT-R),⁵⁵ anxiety/depression (Hospital Anxiety and Depression Scale; HADS),⁵⁶ positive emotions (Positive and Negative Affect Schedule; PANAS),⁶⁵ health-related quality of life (MOS Short Form-12; SF-12),⁵⁷ cardiac symptoms and heart failure-related quality of life (Kansas City Cardiomyopathy Questionnaire; KCCQ),^{58,59} medication adherence (Self-Reported Medication Adherence [adapted from the Heart and Soul Study]; SRMA),⁶⁰ and sodium intake (Scored Sodium Questionnaire; SSQ).⁶¹ Participants will also answer questions about their alcohol (using the AUDIT-C)⁶² and cigarette use. In sum, these scales should take approximately 30 minutes to complete.

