Follow-up phone call (Week 10). At Week 10, a member of the study staff will call participants to repeat the self-report questionnaires that were administered at baseline. These questionnaires assess optimism (LOT-R), positive emotions (PANAS), overall health behavior adherence (MOS SAS), anxiety/depression (HADS), health-related quality of life (SF-12), cardiac symptoms and heart failure-related quality of life (KCCQ), medication adherence (SRMA), and sodium intake (SSQ). Participants will also be asked about alcohol use (AUDIT-C), cigarette smoking, cardiac-related hospital readmissions, and cardiac rehabilitation, and to rate their overall satisfaction with the treatment they received for their cardiac condition over the last 10 weeks on a scale of 0 (not at all satisfied) to 10 (completely satisfied). Finally, patients will be asked about their experience in the study, including any aspects of the intervention or study procedures that could be improved, during follow-up assessment. In sum, these scales should take approximately 30-40 minutes to complete. If participants would rather complete the follow-up questionnaires in written form rather than over the phone, we will send them a paper packet at the time of the follow-up.

Training. [name] (PI) and [name] (LICSW) have substantial experience in explaining and delivering PP exercises from their studies in cardiac and psychiatric patients. The PP exercises for this trial have been identified via published literature,^{33,65-68} or directly from researchers, and modified appropriately for this population. Additional text outlining the rationale and instructions for each exercise are located in the written packets for each exercise that are provided to participants. [name] and [name] will engage in several training exercises prior to study initiation. Together, they will review the treatment manual and our team's prior training manuals related to these exercises. They then will complete all exercises together to gain experience performing and reviewing each exercise.

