[name] and [name] also have significant experience with providing guidance and motivation towards goal-setting from the ongoing work in cardiac patients. [name] currently is the Project Director of another study examining the efficacy of PP and goal-setting interventions in patients with ACS, and [name] serves as an interventionist for that same study. The goal-setting portion of the intervention aims to improve health behaviors that studies have shown to be critical for cardiac health in patients with HF.⁶⁻¹² Similar to their training related to the PP exercises, [name] and [name] will review the treatment manual for this project and complete each exercise together to gain experience providing education and setting goals related to physical activity, sodium restriction, and medication adherence.

Table 1. Schedule of study events.

	Pre-enrollment	Baseline and Initial Visit	Phone Sessions (Weeks 2-10)	Follow-up Phone Call (Week 10)
Cognitive screen	X			
Chart review to confirm eligibility	X			
Assessment of inclusion criteria (MOS SAS, NYHA class)	X			
Chart review for baseline characteristics		X		
PP exercise		X	X	
Goal-setting exercise		X	X	
Exercise ratings		X	X	
Self-report measures (SSQ, LOT-R, PANAS, HADS, KCCQ, SRMA, SF-12)		X		X
Objective adherence data (ActiGraph step counter)		X		X

B. Drugs to be used

No specific medications are being studied or administered solely for research purposes in this study.

C. Devices to be used

No specific devices are being studied or administered solely for research purposes in this study.

D. Procedures/ surgical interventions

No procedures or surgical interventions will be performed solely for research purposes in this study.

E. Data to be collected (See Table 1)

Baseline Data: Participants will complete the MOS SAS, SSQ, LOT-R, PANAS, HADS, KCCQ, SRMA, and SF-12 in person and will receive an Actigraph accelerometer. They will be asked

to begin wearing the accelerometer after their initial. Using the accelerometer in this phase of the study will allow us to test its feasibility and identify any potential problems with its use.

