- Patient rating of immediate outcomes on 10-point Likert scale: Ease of completion, overall utility, change in optimism from pre- to post-exercise.

The PP exercises will be considered to be acceptable if participants have mean scores of at least 6/10 on the ratings of ease of completion and subjective helpfulness across exercises. The PP exercises will be considered to have adequate impact if participants rate optimism significantly higher post-exercise than pre-exercises across exercises (via one-sample t test).

Aim #3 and Exploratory Aim (Impact on psychological outcomes, functional outcomes, and health behaviors): To determine whether the PP intervention is linked to improvements in psychological well-being, functioning, and health behavior adherence from baseline to 10 weeks.

Measures:

- Optimism: LOT-R (primary measure for this aim)
- Positive emotions: PANAS
- Anxiety/depression: HADS
- HF-related QoL: KCCQ
- Health related quality of life: SF-12
- Self-reported adherence: MOS SAS
- Physical activity: ActiGraph accelerometer
- Medication adherence: SRMA
- Sodium intake: SSQ

We will consider the PP intervention to show promise for improving psychological well-being if mean scores on all psychological outcome measures are superior at 10 weeks compared to baseline. Given that this small trial is focused primarily on feasibility, we have set a low bar for improvement (i.e., even slight pre-post improvement). If these basic pre-post improvements did not occur, it would be important to reassess the intervention before moving on. We will move to a next-step trial once we have developed an intervention that appears to be feasible, to match hypotheses generated by our qualitative research, and to have some impact on optimism/positive affect based on a very small sample. Similarly, we will consider the intervention to show promise for improving other outcomes if there are pre-post improvements in the medical/functional outcomes.

C. Statistical methods

Data will be downloaded from REDCap into the Stata statistical package. For Aims 1 and 2 (feasibility, acceptability, and immediate impact), descriptive statistics will be used to report proportion of exercise completion and mean scores on exercise ratings. Differences between pre- and post-optimism scores will be compared using paired t tests.

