We will provide explicit instructions regarding the use of the accelerometer and step counter to ensure safety and proper use, and to reduce inconvenience/distress associated with uncertainty about their safety or use. We will reduce technological failure by educating study participants and providing a technical help line as noted above. The scientific team (i.e., [name], the PI) will liaise with participants regarding any battery problems or technical advice on the Actigraph accelerometer, step counter, and related equipment.

D. Psychosocial risks

Confidentiality. As with any study, there is the risk of a breach of confidentiality; these risks will be minimized by using participant numbers rather than identifying personal data on study documents, and by using locked cabinets/offices and password-protected databases to store personal information. Only study staff (the PI, the research assistant entering data, and the research assistant doing follow-up assessments) will have any access to personally identifiable information about participants, and such access will be limited only to information necessary to complete study tasks.

All data regarding the objective adherence devices will be encoded only with the study participant number that is linked to personal identifying information in the study database. The devices will not be marked with any personal identifiable information, and the database that will be used to monitor accelerometer data will only contain participant numbers. The accelerometers do not record or link participants’ names with their data, and accelerometer data will only be accessed from a locked Partners computer in Warren 1226.

We will ensure that contact with participants is confidential by using only the phone numbers and other contact information that are specifically allowed by the participants and not leaving study-related messages for participants unless expressly allowed by participants. Upon enrollment, we ask all

participants if it is acceptable to leave voice messages on their phones, as well as the appropriate times to call them. We adhere to any and all patient requests regarding contact.

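### Nothing keeps the questionnaire mode the same at baseline and Week 10, so the uncontrolled self-report changes can include a mode effect of unknown size and direction

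*Combined protocol and SAP*

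**What the plan says.** **Baseline.** Section V.E (Baseline Data) gives one mode and no exception: "Participants will complete the MOS SAS, SSQ, LOT-R, PANAS, HADS, KCCQ, SRMA, and SF-12 in person and will receive an Actigraph accelerometer". Section V.A (Initial visit) is labelled as in person, but its list of settings ends with a telephone option: "or over the phone (if a participant prefers to not come to the hospital for an in-person visit". Section III.B (Outpatient recruitment) goes further: "Note: If a participant prefers to perform all study visits by phone, a consent form will be mailed to the participant". In none of these places does the plan say whether participants fill in the forms themselves or have the items read to them.

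**Week 10.** Section V.A (Follow-up phone call) says: "At Week 10, a member of the study staff will call participants to repeat the self-report questionnaires that were administered at baseline". It then offers an alternative at the participant's choice: "If participants would rather complete the follow-up questionnaires in written form rather than over the phone, we will send them a paper packet". That choice is not tied to the mode used at baseline.

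**Decision rule and analysis.** Section VI.A and B calls the intervention promising for psychological well-being if the mean on every psychological measure is better at 10 weeks than at baseline. On the size needed it says: "we have set a low bar for improvement (i.e., even slight pre-post improvement". Other outcomes need only a pre-post improvement. Section VI.C specifies paired t tests with no term for mode. There is one arm and no randomization (IV.C).

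**The concern.** Answers on mood, optimism, adherence and quality of life can depend on whether a person writes them down, says them face to face or says them over the telephone. If the mode differs between the two time points, the pre-post difference contains the mode effect as well as any real change. A concurrent control group with the same schedule would carry the same mode effect and allow it to be subtracted. This study has none.

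The rule has no margin above zero to absorb a small artifact, and it has consequences. Section VI says that without these basic improvements the team would need to reassess the intervention before moving on. A mode shift in the favorable direction could make an inert program look promising. One in the other direction could hold back a useful program.

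The affected measures are the Aim 3 scales (LOT-R, PANAS, HADS) and the self-report exploratory scales (KCCQ, SF-12, SRMA, SSQ, MOS SAS). The primary feasibility aim and the accelerometer step counts do not depend on questionnaire mode.

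**Working it through.** **Step 1: possible mode pairings under the text.**

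- In person at baseline, telephone at Week 10: mode changes. This is the default path in V.E and V.A.
- In person at baseline, paper at Week 10: the setting changes. Whether the form of response changes depends on how baseline was done, which is not stated.
- Telephone at baseline, telephone at Week 10: no change.
- Telephone at baseline, paper at Week 10: mode changes.

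The plan gives no expected share for any pairing. V.E (in person only) and the telephone options in III.B and V.A do not agree and need reconciling.

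**Step 2: what the plan quantifies.** It states no size for a mode effect and no SD for any change score. Section VI.D disclaims power, so there is no figure of the plan's own to reproduce. What follows is a sensitivity illustration.

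**Step 3: inputs.**

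- From the documents: n = 10 completers (VI.D). The rule is a better mean on all psychological measures, by any amount (VI.A and B).
- Counted from V.E: four scores, namely LOT-R, PANAS positive affect, HADS anxiety and HADS depression.
- Assumed: no true change; normal changes; a mode shift m, in SDs of the change score, equal on all four scores (positive is favorable); a share s of completers changing mode; a common correlation r between the four changes.

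**Step 4: formulas.** The standardized mean change on each score is centered at mu = s × m × √10.

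- One score: P = Φ(mu).
- All four: P = ∫ Φ((mu + √r·w)/√(1−r))⁴ φ(w) dw.

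Checks with no shift: at r = 0 the all-four result is 0.5⁴ = 6.3%, and at r = 0.5 it is 1/(4+1) = 20%.

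**Step 5: results.**

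| Share changing mode | Shift m | mu | One score improves | All four improve, r = 0.5 | All four, r = 0 to 0.7 |
|---|---|---|---|---|---|
| any | 0 | 0 | 50.0% | 20.0% | 6.3% to 27.1% |
| all | +0.2 | 0.632 | 73.6% | 45.9% | 29.4% to 53.1% |
| all | −0.2 | −0.632 | 26.4% | 5.6% | 0.5% to 9.6% |
| half | +0.2 | 0.316 | 62.4% | 31.9% | 15.2% to 39.5% |
| half | −0.2 | −0.316 | 37.6% | 11.2% | 2.0% to 17.0% |

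The all-four columns correspond to the Aim 3 rule. The one-score column applies to a single exploratory scale read by itself.

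**The case against.** The strongest reply is that this is a very small feasibility study that openly sets a low bar, claims no power and says the scales are included partly to see whether they can be used in this population. Its primary aim and its primary health-behavior measure (steps) are untouched. The lack of a control and of a margin are larger limits, and mode is only one possible contributor. This stands, and it is why the priority is low.

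Four stronger readings are tempting, and the documents do not support them.

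- *Most participants change mode.* In person is the default, but outpatients may do every visit by telephone and no split is given. Participants seen on the inpatient unit do change mode by default, but their number is not stated either.
- *The shift favors the intervention.* No direction is given. If baseline items were read out face to face, a telephone call might be less exposed to social desirability. If they were self-completed, Week 10 paper may be the closer match. Any wish to please after ten weeks of calls comes from contact with the program, and matching modes would not remove it.
- *The assessor also changes.* Section VII.D mentions "the research assistant doing follow-up assessments", but in a list of who may see identifiable data. V.A says only that study staff make the call, and it describes the trainer as study staff too.
- *Improvement on any one scale is enough.* Slight improvement is enough on each scale, but for the psychological outcomes all of them must improve. With no shift that is a 6% to 27% event over the correlations shown, not 50%.

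**Conclusion.** The point holds in limited form. For participants assessed in person at baseline, the plan's default is a different mode at Week 10, and nothing in it matches, records or accounts for that. The self-report comparisons in Aim 3 and the exploratory aim therefore combine a possible mode effect with any intervention effect, and a single-arm design cannot separate the two.

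The size is unknown. Under the stated assumptions, a shift of 0.2 SD either way moves the chance of meeting the all-measures rule from about 20% to about 46% or 6% if everyone changes mode, and to about 32% or 11% if half do. These figures show that the rule is sensitive to small shifts. They do not show that such a shift exists or which way it would go. For anyone assessed by telephone both times, the mode effect is zero. Priority: minor.

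**What to change.** In V.A, state how the baseline questionnaires are administered, and use the same form of administration (interviewer-read or self-completed on paper) at both times for each participant. For example, staff read the scales aloud at baseline and again on the Week 10 call, and Week 10 paper goes to those who completed paper forms at baseline. Allow another mode only to avoid missing data.

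Bring V.E into line with the telephone options in III.B and V.A.

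Record the mode at each time point and describe any switches alongside the overall change. With about 10 completers this is description only; a subgroup comparison would not be interpretable.

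This matches the form of response but not the channel. Reading aloud face to face and by telephone may still differ, and the recorded mode lets a reader see how many participants that concerns.

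The cost is some protocol wording and a mode field completed at each time point, with no extra staff. The baseline visit may run somewhat beyond the roughly 30 minutes planned for the scales if they are read aloud, and participants have less free choice of mode at Week 10.

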A. Inclusion/Exclusion Criteria

Inclusion criteria:

- Adult patients with NYHA class I, II, or III HF admitted to an MGH inpatient unit or outpatients at the MGH Heart Center.⁴⁹ Patients with NYHA class IV HF have ongoing HF symptoms at rest, making it difficult for them to increase physical activity and other health behaviors; therefore, they will not be included. HF diagnosis will be confirmed via chart review and with the patient's treatment team as needed. NYHA class will be confirmed with the patient and adjudicated by [name] or the patient's treatment team when necessary.
- Suboptimal adherence to health behaviors. This will be defined as a total score of ≤ 15 on three Medical Outcomes Study Specific Adherence Scale (MOS SAS)⁵⁰ items regarding diet/exercise/medications. The MOS SAS has been used in multiple prior studies assessing adherence in cardiac patients, including our own studies in this population.^{40,51,52} This threshold score on the MOS SAS will ensure that all participants will have the potential to improve their health behaviors.

Exclusion criteria:

- Cognitive deficits impeding a participant's ability to provide informed consent or participate, assessed via a 6-item cognitive test that is sensitive and specific for screening for cognitive impairment in research participants.⁵³
- Medical conditions precluding interviews or likely to lead to death within 6 months.
- Inability to speak English, inability to read or write, inability to walk, or lack of a telephone.

Justification for inclusion and exclusion criteria: We will recruit individuals over age 18 that have NYHA class I, II, or III HF and endorse suboptimal adherence to physical activity, diet, and/or medication use. We will study HF because it is extremely common¹ and has been associated with poor functioning²⁻⁵ and high rates of mortality (50% of individuals with HF die within 5 years of diagnosis).⁴ We chose NYHA class I, II, and III HF patients because class II and III patients comprise the majority of participants in studies that identify links between physical activity and improved exercise capacity, quality of life, and survival^{6,8} and because class I patients also likely would benefit from increases in physical activity and health behaviors. We did not include NYHA class IV patients

because they may be too physically impaired to perform some of the PP exercises included in the intervention.

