After completion of the questionnaires, participants will be provided with a treatment manual, with weekly PP exercises and information to teach participants about the importance of health behaviors and set goals to improve these behaviors. They also will receive a copy of *Learning to Live with Heart Failure*,⁶³ a practical guide which is provided by MGH to all HF patients admitted to a cardiology unit at MGH.

The trainer then will introduce the participant to the PP and goal-setting portions of the intervention. For the PP portion, participants will be assigned the first exercise (gratitude for positive events) and will be instructed to perform the exercise within the next week. Prior to completing the exercise, participants will be asked to rate their current level of happiness and optimism, using a 10-point Likert scale. Immediately after completing the exercise, participants will rate the ease of exercise completion, overall utility of the exercise, and their current levels of happiness and optimism, all using 10-point Likert scales. For the first goal-setting session, the trainer will discuss the importance of physical activity in HF. Participants will be given a pedometer, which participants will use to monitor the number of steps they take daily over the following week. The trainer will instruct them in its use and set a goal for monitoring their baseline physical activity over the next week. This pedometer will not be used as an outcome measure but simply will be a tool that participants can use to monitor their activity. We anticipate that this portion of the visit will take approximately 20 minutes.

After assigning the first week’s PP and goal-setting exercises, participants will receive an Actigraph GT3X+ accelerometer, and its use will be demonstrated by the trainer. We will measure activity at baseline (for 7 days) and in the 7 days following the 10-week assessment (we will send participants the ActiGraph in the mail at the appropriate time). In contrast to the pedometer, which is used for participants to monitor their activity, the ActiGraph accelerometer provides no information to

participants about their physical activity and will only be used by the study team to measure physical activity as an outcome.

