Physical activity will be measured using the ActiGraph GT3X+ three-axis accelerometer (ActiGraph, LLC, Pensacola, FL). Accelerometers are often considered to be the standard for measuring habitual physical activity.^{71,72} ActiGraph GT3X+ step counters are validated as measures of physical activity and have been used in numerous studies of physical activity in patients with medical illness.⁶⁴ We chose to use ActiGraph GT3X+ accelerometers because they are the most widely used monitors for research purposes and adequately discriminate between different levels of activity.^{73,74} In this trial, participants will wear the accelerometer (for 1 week at baseline and 1 week at follow-up) to assess the feasibility of doing so and to ensure adequate capture of physical activity. We will measure the number of steps taken daily for the last 7 days they wore the device to ensure that this will provide us with adequate information for subsequent trials. We will turn off all notifications on the device prior to the start of the study. We will require at least 480 minutes of wear time to be considered a valid day,

and at least 5 valid days for a participant's data to be considered complete. If a participant does not provide at least this much data, we will ask the participant to re-wear the step counter until information from at least 5 valid days has been captured.

(b) Medication adherence. We will assess medication adherence using a self-report medication adherence (SRMA) measure. Specifically, we will ask participants what percent of the time (in 10% increments) they took all of their medications as prescribed in the past week and in the past 2 weeks. These questions were adapted from the adherence measure used in the Heart and Soul Study.⁶⁰

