(c) Dietary adherence. We will assess sodium intake over the past month using the Scored Sodium Questionnaire (SSQ).⁶¹ This scale assesses the frequency with which participants consume a variety of sodium-containing foods, ranging from "Rarely or Never Eaten" to "At Least Once Daily." Total SSQ score has been shown to correlate significantly with 24-hour urinary sodium, and the SSQ has been validated in patients with significant medical illness.⁶¹ If participants are hospitalized, they will be asked to describe their sodium intake prior to admission, given that their diet in the hospital may be significantly different than their typical diet at home. The SSQ will be completed both at baseline and again at the 10-week follow up.

(d) Self-reported adherence. We will assess self-reported adherence using the MOS SAS⁵⁰ items regarding diet/exercise/medications. Participants will be asked to rate how often they completed each health behavior over the last month, with choices rating from "none of the time" to "all of the time." The MOS SAS has been used in multiple prior studies assessing adherence in cardiac patients, including our own studies in this population.^{40,51,52}

Measurement of psychological outcomes. We will measure optimism, positive affect and other psychological constructs that may potentially be impacted by the PP-based health behavior intervention that will be tested in subsequent trials. Doing so in this study will allow us to evaluate the feasibility of using these scales in this specific patient population.

(a) Dispositional optimism (primary psychological outcome measure) will be measured using the Life Orientation Test-Revised (LOT-R), a well-validated 6-item instrument. Dispositional optimism is the positive psychological state most linked to cardiac outcomes,^{23,75,76} and the LOT-R has been used to measure optimism in many studies of cardiac patients.⁷⁷⁻⁷⁹ Though dispositional optimism theoretically would be stable over time, research suggests that LOT-R scores can change quickly in response to psychological interventions.^{38,80,81}

(b) Positive affect will be measured using the positive affect items on the Positive and Negative Affect Schedule (PANAS),⁸² a well-validated scale used in other intervention trials and in patients with HF.^{83,84}

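### Ward-enrolled participants may wear the baseline ActiGraph partly in hospital and the follow-up one normally at home, which can inflate the pre-post step change

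*Combined protocol and SAP*

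**What the plan says.** Section III.A admits adults with NYHA class I to III heart failure who are "admitted to an MGH inpatient unit or outpatients at the MGH Heart Center"; it states no split and no cap. Section V.A, on the initial visit, says: "The initial visit will occur in an MGH inpatient unit, in the outpatient cardiac clinic", among other places. At that visit "participants will receive an Actigraph GT3X+ accelerometer, and its use will be demonstrated by the trainer". Section V.E (Baseline Data) then asks participants "to begin wearing the accelerometer after their initial". The sentence ends there without its noun, but Table 1 places the ActiGraph in the column for baseline and the initial visit.

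The two windows are set in Section V.A: "We will measure activity at baseline (for 7 days) and in the 7 days following the 10-week assessment". Section V.E, item (a) on physical activity, adds: "We will measure the number of steps taken daily for the last 7 days they wore the device" and "We will require at least 480 minutes of wear time to be considered a valid day". Five valid days make a record complete, and a participant with fewer is asked to wear the device again. Section VII.C has the device mailed back after 7 days. None of these rules mentions setting or discharge.

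For sodium the protocol does deal with hospital stay. Section V.E, item (c), asks hospitalized participants about intake before admission, "given that their diet in the hospital may be significantly different than their typical diet at home".

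The trial has one arm (Section IV.C). Section VI.C compares baseline with week 10 by paired t tests without adjustment. Section VI.A and B treats pre-post improvement as the sign of promise for the functional and other outcomes.

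**The concern.** If part of the baseline week is spent on a ward and the follow-up week is spent at home, the two step counts differ in setting as well as in time. A person whose activity at home has not changed can then show a gain because the low-activity ward days fall only on the baseline side. The protocol accepts this reasoning for diet but has no matching rule for steps.

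Nothing later in the plan separates the two explanations. There is no control arm, the analysis ignores recruitment setting, and the baseline variables listed in Section V.E include neither recruitment setting nor discharge date. Because the bar is any improvement, even a modest artefact can tip the reading of the measure that the protocol names as its main health behavior outcome.

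**Working it through.** The documents state no effect size, standard deviation or power for steps, so there is no planned figure to reproduce. The check has two parts.

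**Do ward days count?** The initial visit may be on the ward. The device is handed over there. On the natural reading, wear starts after that visit. A day is valid on wear time alone. So a ward day with 480 minutes of wear is a valid baseline day. No rule in the plan removes it.

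**How large could the effect be on the trial mean?** From the documents: a 7-day window and 10 completers (Section VI.D). Assumed, because the documents are silent: *m* inpatients among the 10 completers (2, 5 or 8), *d* ward days in the baseline week (2, 4 or 7), and *r*, ward steps as a fraction of home steps (0.8, 0.6 or 0.4). Also assumed: home steps *H* are the same for everyone and do not change, follow-up is all at home, and the intervention has no effect.

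- Baseline mean = *H*(1 − *a*), with *a* = (*m*/10) × (*d*/7) × (1 − *r*).
- Follow-up mean = *H*.
- Apparent rise = *a*/(1 − *a*).

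Putting the numbers in:

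- Low: *a* = 0.2 × 2/7 × 0.2 = 0.0114; rise = 0.0114/0.9886 = 1.2%.
- Middle: *a* = 0.5 × 4/7 × 0.4 = 0.1143; rise = 0.1143/0.8857 = 12.9%.
- High: *a* = 0.8 × 7/7 × 0.6 = 0.48; rise = 0.48/0.52 = 92.3%.

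With *m* = 0 or *d* = 0, *a* = 0 and the rise is zero.

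**How often would the result point upward?** A simulation of the paired t test (10 participants, 40,000 runs, no true effect) used an assumed SD of change, expressed as a share of home steps.

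| Case | SD of change | Chance that mean change > 0 | Chance of a significant rise |
|---|---|---|---|
| No ward days | 30% or 50% | about 0.50 | about 0.025 |
| Low | 30% | 0.55 | 0.03 |
| Middle | 30% | 0.89 | 0.16 |
| Middle | 50% | 0.77 | 0.09 |
| High | 30% | 1.00 | 0.97 |

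**What would offset it?** The baseline week also contains the first activity session and pedometer monitoring. If these raise every counted baseline day by a fraction *b*, and follow-up is not raised in the same way, the baseline mean becomes *H*(1 − *a*)(1 + *b*). The artefact then cancels when *b* = *a*/(1 − *a*), that is, 12.9% in the middle case. The documents give no value for *b*.

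**The case against.** The strongest reply has four parts.

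*The start of wear is inferred.* The key sentence is incomplete, and a patient enrolled on the day of discharge would wear the device at home. This stands. The plan permits ward wear; it does not state that it will happen.

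*Existing rules may move counted days toward home.* Steps are taken from the last 7 days worn, and re-wear is available. This helps only a little. Planned wear is 7 days and the device goes back after 7 days, so the last 7 are normally the same 7. Re-wear is triggered by too few valid days, and valid ward days prevent the trigger.

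*The net direction is not fixed.* The pedometer and activity session in the same week may raise baseline steps. This stands as a possible partial offset of unknown size. The week-1 goal is monitoring; the behavioral activity goal comes in Week 2. An opposing bias would not make the baseline a clean measure of usual activity.

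*Little depends on it.* Steps fall under the Exploratory Aim. The accelerometer criterion in Aim 1 concerns valid days at 10 weeks, and the move to a next-step trial rests on feasibility, fit with the qualitative work and some impact on optimism or positive affect. This stands and limits the weight of the point. What remains exposed is the reading of promise for physical activity.

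**Conclusion.** The point holds as a gap in the measurement plan: followed as written, the plan can place ward days in the baseline week and so can inflate the pre-post step change. Under the assumed ranges, the spurious rise in the trial mean runs from about 1% to 92%, and it is zero if no inpatients enrol or all enrol at discharge. Every input except the 7-day window and the 10 completers is an assumption, so the range shows sensitivity and is not an estimate.

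Three stronger readings are tempting and are not supported:

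- A reader might infer that discharge necessarily raises the outcome. The documents give no ward or home step counts, inpatient share or length of stay, and the week-1 content may work the other way.
- A reader might take the distortion for one ward-enrolled participant as the bias in the trial result. In the middle case the individual share is 4/7 × 0.4 = 0.2286, an apparent rise of 0.2286/0.7714 = 29.6%, against 12.9% for the trial mean when half are inpatients.
- A reader might infer that the trial's main conclusion is at risk. The feasibility aim and the stated criteria for going forward do not use baseline steps.

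This is a cheap improvement to an exploratory measure.

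**What to change.** In Sections V.A and V.E:

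1. Complete the sentence on when baseline wear starts.
2. State that days spent in hospital are not valid days at baseline or follow-up, so that an inpatient's baseline is counted from the first full day after discharge. Use the existing re-wear rule to reach 5 valid days.
3. Where possible, complete baseline wear before the Week 2 activity-goal session.
4. Record the discharge date and the setting of each wear day.
5. In Section VI.C, report step change separately by recruitment setting. Excluding ward days removes the ward-wear artefact, but recovery after an admission remains confounded with the intervention.

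The cost is a few sentences and two recorded items. For ward-enrolled participants, baseline wear and device return come a few days later, and part of the baseline may overlap more of the early intervention. The timing is tight. The first call is scheduled one week after the initial visit, so a 7-day window with two excluded days leaves 7 − 2 = 5 valid days, exactly the minimum. With three or more excluded days, re-wear would run past that call unless the session is timed to follow it, which is why item 3 can only be a preference.
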